9.2 Subject Accountability

The number of subjects screened, randomized, receiving IP, and completing the study will be summarized. Key study dates for the first subject enrolled, last subject enrolled and last subject's end of study will be presented.

Study discontinuation and IP discontinuation will be tabulated separately by reasons for discontinuation.

The number and percent of subjects randomized will be tabulated by the stratification factor.

9.3 Important Protocol Deviations

Important Protocol Deviations (IPDs) categories are defined by the study team before the first subject's initial visit and updated during the IPD reviews throughout the study

prior to database lock. These definitions of IPD categories, subcategory codes, and descriptions will be used during the course of the study. Eligibility deviations are defined in the protocol.

Protocol deviations and important protocol deviations will be categorized by the Clinical Research Physician (CRP). A list of protocol deviations and important protocol deviations for all subjects for week 16 analysis will be defined prior to the Week 16 data restriction and unblinding (i.e., prior to the unblinding of double-blind placebo-controlled phase data). The list of protocol deviations and important protocol deviations for all subjects for final analysis will be finalized prior to the final database lock. This listing of important protocol deviations for week 16 analysis will also identify which subjects are to be excluded from the per-protocol population.

Protocol deviations and important protocol deviations by treatment group and overall will be provided for the placebo-controlled phase for the ITT analysis set, and for the Apremilast extension phase for subjects who receive at least one dose of IP during the phase. Summary tables showing the number and percent of subjects with at least one protocol deviation and important protocol deviations and by each category of protocol deviations and important protocol deviations will be provided. Listings of subjects with protocol deviations and important protocol deviations will also be provided.

Additionally, protocol deviations and important protocol deviations related to COVID-19 will be summarized.

9.4 Demographic and Baseline Characteristics

Summaries for the demographics, baseline characteristics, prior medication/procedure, and concomitant medications/procedure will be presented for the ITT analysis set by treatment group and overall. Subject data listings will also be provided.

9.4.1 Demographics

Summary statistics will be provided for the following continuous variables:

- Age (years)
- Weight (kg)
- Height (cm)
- Baseline Body Mass Index (BMI; kg/m²)

Number and percentage will be provided for the following categorical variables:

- Sex (Male, Female)
- Age category (< 65, \geq 65 years; < 40, \geq 40 to < 65, \geq 65 to < 75, \geq 75 to < 85, \geq 85 years)
- Race (American Indian or Alaska Native, Asian, Black or African American, Native Hawaiian or Other Pacific Islanders, White, Not Collected or Unknown)
- Ethnicity (Hispanic or Latino, not Hispanic or Latino, Not reported, Unknown)
- Baseline weight category (< 50, \geq 50 to < 60, \geq 60 to < 70, \geq 70 to < 85, \geq 85 kg)
- Baseline BMI category (< 18.5, \geq 18.5 to < 25, \geq 25 to < 30, \geq 30 to < 35, \geq 35 to < 40, \geq 40 kg/m²)
- Geographical region (USA/Canada, EU)
- Alcohol usage (Yes, No)
- Tobacco usage (Current user, Past user, Never used)

9.4.2 Baseline or Disease Characteristics

Baseline clinical characteristics will be summarized descriptively by treatment group, which will include the following:

- Duration of genital psoriasis (from date of diagnosis to the date of informed consent; year, presented one digit after the decimal point)
- Duration of genital psoriasis categories (<2, \geq 2 to <5, \geq 5 to < 10, \geq 10 to < 20, \geq 20 years)
- Baseline modified sPGA-G score: Moderate (3), Severe (4)
- Baseline sPGA score: Moderate (3), Severe (4)
- Baseline psoriatic involved BSA (%)
- Baseline BSA (%) category (<10%, \geq 10%)
- Baseline DLQI total score
- Number of prior phototherapies
- Number of failed prior phototherapies for subjects who had prior phototherapies
- Number of prior conventional systemic therapies

- Number of failed prior conventional systemic therapies for subjects who had prior conventional systemic therapies
- Number of prior biologic therapies
- Number of failed prior biologic therapies for subjects who had prior biologic therapies
- Number of prior systemic therapies
- Number of failed prior systemic therapies for subjects who had prior systemic therapies

9.4.3 Medical History

Medical history terms will be coded using the Medical Dictionary for Regulatory Activities (MedDRA) version 24.1 or higher. A frequency summary (counts and percentage) of medical history will be presented by treatment group, system organ class (SOC), and preferred term (PT).

9.4.4 Prior and Concomitant Procedures

Prior and concomitant procedures will be coded using the Medical Dictionary for Regulatory Activities (MedDRA) version 24.1 or higher. Frequency summaries of prior and concomitant procedures will be provided for the safety population by treatment group, SOC, and PT.

Prior procedures are defined as those started before the first dose of IP (whether or not ended before the first dose of IP). Concomitant procedures will be summarized for (1) Placebo-controlled Phase (Weeks 0 to 16), (2) Apremilast Extension Phase (Weeks 16 to 32), and (3) Observational Follow-up Phase (4 weeks). The concomitant procedures will be similarly analyzed as concomitant medications in the next section.

9.4.5 Prior and Concomitant Medications

The Anatomical Therapeutic Chemical (ATC) coding scheme of the World Health Organization Drug Dictionary (WHO DD version March 2020 or higher) will be used to group prior and concomitant medications and prior psoriasis medications into relevant categories. Frequency summaries will be provided by treatment group, ATC 2 level, and standardized medication name for the safety population.

Prior medications are defined as those started before the first dose of IP (whether or not ended before the first dose of IP). Prior medications that continue after the first dose of IP will also be reported as concomitant medications.

Prior psoriasis medications will be classified as phototherapies, biologic therapies, conventional systemic therapies, or systemic therapies through manual review by Clinical Research Physician (CRP).

For each of the treatment phases, concomitant medications are defined as non-study medications started during the phase, or non-study medications started before the phase and ended or remained ongoing during the phase. The treatment phase for concomitant medications will start on the first dose date and end one day prior to the last dose date.

Medications in the Follow-up Phase will include those medications started from the date of last dose of investigational product.

Summaries will be provided for prior psoriasis medications and prior medications, as well as for concomitant medications in: (1) Placebo-controlled Phase (Weeks 0 to 16), (2) Apremilast Extension Phase (Weeks 16 to 32), and (3) Observational Follow-up Phase (4 weeks).

9.5 Efficacy Analyses

9.5.1 Analyses of Primary Efficacy Endpoint(s)

The primary endpoint is the proportions of subjects who achieve modified sPGA-G response at Week 16 (defined as modified sPGA-G score of clear (0) or almost clear (1) with at least a 2-point reduction from baseline at Week 16). The main analysis for the primary efficacy endpoint will be based on the ITT analysis set. A sensitivity analysis using the PP analysis set will also be performed.

The primary endpoint will be analyzed using the CMH (Cochran–Mantel–Haenszel) test adjusting for the stratification factor at randomization. The two-sided p-values from the CMH test, the adjusted treatment difference in proportion using the weighted average of the treatment differences across the strata with the CMH weights, along with the associated two-sided 95% CIs using a normal approximation to the weighted average will be provided.

Missing values at Week 16 for this endpoint will be imputed using the multiple imputation (MI) method (SAS Institute Inc. 2011) based on similar subjects who remained in the study as the primary method. The SAS procedure MI will be used to impute missing modified sPGA-G scores at the scheduled analysis visits in the Placebo-controlled Phase (Weeks 0–16) to create M=50 complete data sets. The missing data patterns will be checked at the scheduled analysis visits, ie, Baseline (Week 0), and Weeks 2, 4, 8,

12 and 16. If there are non-monotone missing patterns, two separate imputation procedures will be used to complete the imputation process.

In the first step, the Markov Chain Monte Carlo (MCMC) method will be used with a single chain to impute missing scores by treatment and stratification factor to create M=50 imputed data sets with monotone missing patterns. In case there are convergence issues, a simple model will be used to impute the missing scores by treatment, with further simplification by dropping both treatment and stratification factor in imputation model if necessary. The seed will be set to 17813721. The imputed scores will be rounded to the nearest integer. The minimum and the maximum values for imputation will be 0 and 4, which correspond to the lowest and the highest modified sPGA-G scores.

In the second step, the predictive mean matching method will be used to impute the remaining missing scores for the 50 data sets with monotone missing patterns. The imputation procedure will use monotone statement to create one complete data set for each of the monotone data set from the first step, and the variables will include treatment arm, stratification factor, and modified sPGA-G scores at scheduled analysis visits from baseline to Week 16. The seed will be set to 55218163. The number of closest observations to be used in the selection will be set to 2.

After the completion of imputation, the modified sPGA-G response at Week 16 will be derived based on both observed and imputed scores. The same CMH method will be used to analyze the 50 complete data sets and the SAS procedure MIANALYZE will be used to combine the results for the statistical inferences.

Shift table for shifts from baseline to post-baseline visits and End of Phase will be provided by treatment and time point for sPGA-G score.

Additional sensitivity analysis will be conducted to account for missing data using the non-responder imputation (NRI) method and the tipping point analyses.

For the tipping point analyses, let M1 and M2 be the total number of subjects with missing data of primary endpoint in Apremilast and Placebo. There are overall $(M1 + 1) * (M2 + 1)$ possible ways for imputing missing data as responders or non-responders in statistical analysis, ranging from imputing all missing values as non-responders to imputing all missing values as responders in each of the two arms. For each of the $(M1 + 1) * (M2 + 1)$ different imputation patterns, the Chi-square test will be used for testing statistical significance and the output can be plotted in a rectangle for inspection. The

staircase region that separates significant and non-significant outcomes forms the tipping-point boundary.

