4.2. Inclusion Criteria

Subjects must satisfy the following criteria to be enrolled in the study:

1. Subject is ≥ 18 years of age at the time of signing the informed consent form (ICF).
2. Subject must understand and voluntarily sign an ICF prior to any study-related assessments/procedures being conducted.
3. Subject is willing and able to adhere to the study visit schedule and other protocol requirements.
4. Subject must have a diagnosis of chronic plaque psoriasis for at least 6 months prior to signing the ICF.
5. Subject must have a diagnosis of moderate or severe psoriasis of the genital area at Screening and Baseline as defined by having a modified sPGA-G score of ≥ 3 (moderate or severe).
6. Subject must have a diagnosis of moderate or severe psoriasis at Screening and Baseline as defined by having a sPGA score of ≥ 3 .
7. Subject must have plaque psoriasis (BSA $\geq 1\%$) in a non-genital area at both Screening and Baseline.
8. Subject must have been inadequately controlled with or intolerant of topical therapy for the treatment of psoriasis affecting the genital area.
9. Subject must be in good health (except for psoriasis) as judged by the investigator, based on medical history, physical examination, clinical laboratories, and urinalysis.
10. Subject must meet the following laboratory criteria:
 - a. White blood cell count $\geq 3000/\text{mm}^3$ ($\geq 3.0 \times 10^9/\text{L}$) and $< 14,000/\text{mm}^3$ ($< 14 \times 10^9/\text{L}$)
 - b. Platelet count $\geq 100,000/\mu\text{L}$ ($\geq 100 \times 10^9/\text{L}$)
 - c. Serum creatinine $\leq 1.5 \text{ mg/dL}$ ($\leq 132.6 \mu\text{mol/L}$)
 - d. Total bilirubin $\leq 2 \text{ mg/dL}$ ($\leq 34 \mu\text{mol/L}$)
 - e. Aspartate aminotransferase (AST) (serum glutamic oxaloacetic transaminase [SGOT]) and alanine aminotransferase (ALT) (serum glutamic pyruvic transaminase [SGPT]) $\leq 2 \times$ upper limit of normal (ULN)
11. Females of childbearing potential (FCBP)[†] must have a negative pregnancy test at Screening and Baseline. While on investigational product and for at least 28 days after taking the last dose of investigational product, FCBP who engage in activity in which

conception is possible must use one of the approved contraceptive^s options described below:

Option 1: Any one of the following highly effective methods: hormonal contraception (oral, injection, implant, transdermal patch, vaginal ring); intrauterine device (IUD); tubal ligation; or partner's vasectomy;

OR

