4.1 Planned Covariates

Covariates includes but not be limited to baseline value for each measured endpoint.

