4.2 Subgroups

Subgroup analysis will be carried out for modified sPGA-G response at Week 16 based upon baseline demographics and disease characteristics. Summary and analysis will be based on ITT population and missing values will be imputed using MI method.

The following subgroup variables will be used:

- Baseline BSA (%) category (<10%, ≥10%)
- Baseline modified sPGA-G score (moderate [3] or severe [4])
- Sex (Male, Female)
- Race (White, Non-white)
- Age category (<65 years, ≥ 65 years)
- Alcohol usage (Yes, No)
- Tobacco usage (Current user, Past user, Never used)
- Geographical region (USA/Canada, EU)
- Baseline weight category (< 50, ≥ 50 to < 60, ≥ 60 to < 70, ≥ 70 to < 85, ≥ 85 kg)

- Baseline BMI category (< 18.5, ≥ 18.5 to < 25, ≥ 25 to < 30, ≥ 30 to < 35, ≥ 35 to < 40, ≥ 40 kg/ m²)
- Duration of genital psoriasis categories (<2, ≥2 to <5, ≥5 to < 10, ≥ 10 to < 20, ≥ 20 years)
- Prior conventional systemic therapies (Used or Never used)
- Prior phototherapies (Used or Never used)
- Prior biologic therapy (Used or Never used)

5. Definitions

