8.4 Detection of Bias

This study has been designed to minimize potential bias by the use of randomization of subjects into treatment groups and the use of blinding. Other factors that may bias the results of the study include:

- Major protocol deviations likely to impact the analysis and interpretation of the efficacy endpoints
- Subject level unblinding before final database lock and formal unblinding

Important protocol deviations likely to impact the analysis and interpretation of the efficacy endpoints will be tabulated in the Clinical Study Report (CSR).

Any unblinding of individual subjects prior to formal unblinding of the study will be documented in the CSR. The impact of such unblinding on the results observed will be assessed.

Additional sensitivity analyses may be included to assess the impact of potential biases on the primary endpoint. If any sensitivity analyses are required to evaluate potential biases in the study's conclusions, then the sources of the potential biases and results of the sensitivity analyses will be documented in the CSR.

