9.5.1.1 Assessing Study Site Effect

The primary endpoint will be assessed for site effect.

This study is a multicenter study and planned to have approximately 50 sites to enroll and randomize 286 subjects. A single site may not have sufficient number of subjects to allow meaningful within-site analysis of treatment effects stratified by baseline BSA category; therefore, study sites effect will be assessed by pooling sites on geographic basis to help interpret the results.

In pooling sites for analysis, the minimum cell size of 5 randomized subjects per treatment arm (placebo arm or apremilast arm) per stratum of baseline BSA (%) category (< 10% or \geq 10%) will be used. The pooling strategy is described as follows: 1) Sites will be pooled within each region (USA/Canada or EU) according to their rank based on site-specific sample size, starting with the smallest sites; i.e., within a region, the smallest sites will first be pooled until the pooled site has a minimum cell size of 5 for each of the four cells. 2) The remaining un-pooled sites will then be pooled within the region with the smallest pooled site. 3) In the rare case that all site pooled together in a region does not satisfy the above condition (a minimum cell size of 5 for each of the four cells), all sites in the region will be pooled together with the smallest pooled site of the other region.

Sites will be pooled together as described above in order to assess the site effect and site by treatment interaction on the primary efficacy endpoint.

For the pooled sites, summary and analyses will be based on ITT analysis set using MI imputation for missing values. Study site effect will be assessed for the primary endpoint by stratifying the analysis based on pooled site in addition to the stratification factor at randomization and examining whether the treatment differences adjusted for both stratification factor and pooled site are consistent with those from the primary analysis.

In addition, the consistency of the treatment effect across individual study sites (or pooled sites) will be assessed by performing a subgroup-type analysis with respect to the endpoints, with individual study sites (or pooled sites) treated as subgroups. Listings of response rates will be provided by individual study site and by pooled site. The treatment difference for each of the individual study sites (or pooled sites) will be reviewed to determine the effect among the individual study sites (or pooled sites).

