9.5.2.2 Continuous Variables

The continuous variables for secondary endpoints include the following:

- Change from baseline in affected BSA at Week 16
- Change from baseline in DLQI total score at Week 16
- Change from baseline in GPSS total score and individual items scores at Week 16

The continuous efficacy endpoints will be analyzed based on the ITT analysis set using a mixed-effect model for repeated measures (MMRM) as the primary method. The MMRM model will use the change from baseline as the response variable and include treatment group, visit time, treatment-by-time interaction, and stratification factor as fixed effects, and the baseline value as a covariate. An unstructured covariance matrix will be used to model the correlation among repeated measurements. The Kenward-Roger adjustment will be used with restricted maximum likelihood (REML) to make proper

statistical inference. Within-group least-squares (LS) means and the associated SEs and 2-sided 95% CIs, treatment difference in LS means and the associated SEs and 2-sided 95% CIs and 2-sided p-values will be derived from the MMRM model for Week 16 and other scheduled visits (Week 2, 4, 8, and 12, if applicable) in the model.

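### Should the primary analysis of modified sPGA-G response also adjust for the baseline score (3 versus 4), given that SAP 4.1 lists baseline values as covariates?

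*SAP*

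**What the plan says.** SAP 4.1 is a single sentence: "Covariates includes but not be limited to baseline value for each measured endpoint". It does not say which analyses use these covariates.

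SAP 9.5.2.2 carries it out for the continuous secondary endpoints: the MMRM has treatment, visit, their interaction and the stratification factor as fixed effects, "and the baseline value as a covariate".

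For the primary endpoint, SAP 9.5.1 specifies a CMH "test adjusting for the stratification factor at randomization", and Protocol 9.6.1.1 says the same. The only stratification factor is baseline BSA, below 10% or at least 10%. SAP 9.5.2.1 treats sPGA response and GPI-NRS response in the same way.

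Baseline modified sPGA-G does appear elsewhere:

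- In the second imputation step of 9.5.1, where "the variables will include treatment arm, stratification factor, and modified sPGA-G scores at scheduled analysis visits from baseline to Week 16".
- In the shift table from baseline, also in 9.5.1.
- As a subgroup variable (3 or 4) in SAP 4.2, in ITT with multiple imputation.
- In the baseline table of SAP 9.4.2, by treatment group.

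The site-effect analysis in 9.5.1.1 works "by stratifying the analysis based on pooled site in addition to the stratification factor at randomization" and does not add the baseline score. SAP 8.4 leaves further work open: "Additional sensitivity analyses may be included to assess the impact of potential biases on the primary endpoint".

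**The concern.** Protocol 4.2 admits only subjects with a modified sPGA-G of 3 or 4, and response means a score of 0 or 1 with a fall of at least 2 points. From 3 that is a fall of 2 or more; from 4 it is a fall of 3 or more. The definition therefore gives a structural reason to expect fewer responders among severe subjects. Randomization is not stratified by this score, so its balance is left to chance.

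With SAP 4.1 beside this, a reader could conclude that a planned covariate was dropped from the analysis that matters most. Two things would be at stake: a somewhat wider interval than necessary, and no pre-agreed adjusted estimate if the baseline table shows more severe subjects in one arm. An adjustment chosen after unblinding would be open to the charge of being post hoc.

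**Working it through.** **The plan's own figure.** Inputs from SAP 3.2: 25% versus 10%, 143 per arm, 20% dropout, two-sided 0.05, chi-square test. Evaluable per arm: 143 × 0.8 = 114. The mean rate is 0.175.

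z = [0.15·√114 − 1.96·√(2 × 0.175 × 0.825)] / √(0.25 × 0.75 + 0.10 × 0.90) = (1.602 − 1.053) / 0.527 = 1.04, so power is 85.1%.

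The stated 85% reproduces and does not depend on any covariate. With all 143 per arm counted, the same formula gives 92.0%.

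**Assumptions the documents do not supply.** Severe share *s* from 10% to 50%. Ratio *r* of severe to moderate response from 0.25 to 1.0, the same in both arms. Overall rates are held at 25% and 10%.

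**Exposure to chance imbalance.** In an arm with overall rate *p*, the moderate rate is p/(1 − s + s·r) and the severe rate is *r* times that.

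- Example, s = 20%, r = 0.5. Apremilast: 0.25/0.9 = 27.8% moderate and 13.9% severe, a gap of 13.9 points. Placebo: 11.1% and 5.6%, a gap of 5.6 points. The average gap is 9.7 points.
- SD of the between-arm difference in severe share: √(2 × 0.2 × 0.8/143) = 4.73 points.
- A 1-SD imbalance therefore shifts the treatment difference by 0.0473 × 9.7 = 0.46 points.
- SE of the difference: √(0.2775/143) = 4.41 points. The shift is 0.46/4.41 = 0.10 SE.
- At the strong end, s = 50% and r = 0.25, the average gap is 21 points and the SD is 5.91 points. The shift is 1.24 points, or 0.28 SE.

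The square of this ratio is the share of variance that adjustment could remove at best: 0.104² = 1.1% and 0.282² = 7.9%. Extra strata cost some of that. In simulation, with severe shares of 20-50%, the net variance reduction was 2-7% at r = 0.25 and 0.4-1.8% at r = 0.5. At r = 0.75-1.0 the variance rose by 0.3-0.9%.

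**Power.** CMH with BSA × baseline score (four strata) against BSA only; 400,000 simulated trials per setting; complete data; 40% with BSA ≥10%; BSA not prognostic. The two BSA strata within a score level are merged if either has fewer than 10 subjects in an arm. BSA-only power is 92.6-92.8% with 143 per arm and 86.0-86.2% with 114. Change in points:

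| Per arm | Severe share | r = 0.25 | 0.5 | 0.6 | 0.75 | 1.0 |
|---|---|---|---|---|---|---|
| 143 | 20% | +0.52 | +0.13 | −0.01 | −0.10 | −0.19 |
| 143 | 30% | +0.83 | +0.18 | +0.07 | −0.11 | −0.21 |
| 143 | 40% | +1.21 | +0.29 | +0.08 | −0.13 | −0.20 |
| 143 | 50% | +1.55 | +0.36 | +0.14 | −0.11 | −0.19 |
| 114 | 20% | +0.68 | +0.12 | −0.03 | −0.19 | −0.30 |
| 114 | 30% | +1.15 | +0.25 | −0.02 | −0.25 | −0.36 |
| 114 | 40% | +1.68 | +0.31 | +0.03 | −0.27 | −0.41 |
| 114 | 50% | +2.18 | +0.42 | +0.07 | −0.29 | −0.44 |

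At 10% severe, over both sample sizes, the change is +0.2 to +0.3 at r = 0.25, about 0 at 0.5 and −0.15 to −0.27 at 1.0. Type I error (10% in both arms) is 4.9-5.0% for both tests.

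The r = 0.25 column is a strong assumption: for severe shares of 20-50% it is a within-arm odds ratio of 4.4-6.0, against 2.1-2.5 at r = 0.5. At r = 0.5 with 143 per arm, the four-stratum test gains significance in 0.7-1.1% of trials and loses it in 0.6-0.8%.

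**With imputation.** A simplified run (20% missing completely at random, 50 imputations within arm and baseline score, no intermediate visits) gives the SD of the difference, BSA-only against four strata, at 20% and 50% severe:

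- r = 0.25: 4.94 against 4.90, and 4.90 against 4.76
- r = 0.5: 4.93 against 4.92, and 4.92 against 4.89
- r = 1.0: 4.95 against 4.96, and 4.95 against 4.97

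The pattern is the same.

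**Thin strata.** At 20% severe and 40% with BSA ≥10%, the smallest stratum expects 143 × 0.2 × 0.4 = 11.4 subjects per arm. Some stratum falls below 10 in an arm in 48% of trials with 143 per arm and 84% with 114.

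**The case for a change.** The best case for acting does not rest on power. A supportive CMH analysis that adds the baseline score costs a few lines before Week 16 unblinding, leaves the confirmatory test alone, and follows the format 9.5.1.1 already uses for pooled site. It would give a pre-agreed answer if the arms differ in severe share. A subgroup analysis gives an effect within each level, not an adjusted overall estimate, and the option left open in SAP 8.4 commits the sponsor to nothing.

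The textual part stands: in the visible text, no overall comparison of sPGA-G response adjusts for the baseline score. (SAP 9.5.3 is redacted and parts of 9.7 are not shown, so nothing can be said about those.) What does not follow is a material benefit. A typical chance imbalance moves the estimate by 0.28 SE at most under the assumptions used for the working, and by 0.10-0.16 SE at r = 0.5. A reader who sees an imbalance in the baseline table can judge its effect from the response by baseline score in each arm, which is prespecified in ITT with the same imputation. The precision gain would not reach the confirmatory result at all, because the added analysis would be supportive. Making it primary would replace a protocol-specified test by one that loses up to about 0.4 points of power if the score does not predict response.

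**Conclusion.** No change follows. The BSA-stratified CMH analysis adjusts for the factor used in randomization, keeps its type I error and supports the stated power. Whether to add the baseline score is a fair trade-off with little on either side: about −0.4 to +2.2 points of power over severe shares of 10-50% and response ratios of 0.25-1.0. The larger gains appear only at a ratio of 0.25. Both ranges are assumptions, since the documents give neither quantity. The simulations also assume that BSA is not prognostic, that severe share is independent of BSA and that the ratio is the same in both arms. They cover sPGA-G response; sPGA and GPI-NRS response were not computed separately.

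SAP 4.1 is loosely worded, but it assigns covariates to no analysis, and the analysis sections leave no doubt: the MMRM takes the baseline value and the CMH takes the BSA stratum. An analyst following 9.5.1 and 9.5.2 would program both correctly. Saying in 4.1 which analyses use the baseline value would record this without altering any result.
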